1. Eligibility verification - When patients log into the application, they will verify their name and address as well as their eligibility to participate in the study based on age, part d enrollment, and single representative from their household. (We will not exclude people from accessing the tool based on the single representative but will exclude them from data analysis). They will also identify the Part D plan in which they are currently enrolled.
2. Informed consent
3. Collect contact information - Consented participants will provide their e-mail address, using double-entry verification, and will be informed that further communication regarding the study will be by e-mail rather than by mail.
4. Pre-enrollment survey (Survey 1) - We will ask a few questions intended to provide information on individual characteristics of interest for the purpose of data analysis.

We will consider people who consent through the enrollment app as the “enrolled” population. The enrolled population will be randomly assigned to one of three arms (Treatment A, Treatment B or Control). Within 2 days after subjects enroll, we will send them by e-mail a letter that includes their study ID and information on how to access the tool, including the location of the website, when it will be available and log-in instructions. They will use the study ID to log into the website when open

enrollment begins. Shortly before and close to the end of open enrollment, we will send them another reminder with the same information.

We will provide support to study participants in the form of an e-mail address and a phone number they can call. This information will be available in our study tool, the control arm screen and the consent form. We will indicate that they will receive a response within 48 business hours.

Table 1: Recruitment Objectives

Sample Name	Category	Assumptions	Number of Study Subjects
Eligible for Recruitment	Eligible for recruitment		38,866
Recruited Sample	Chosen for mail recruitment	Derived from assumptions below	10,417
	Check for Eligibility	20% of those who contacted by mail check their eligibility	2,083
Enrolled Population	Enroll in Study	Assume 40% attrition among those who access enrollment app	1,250
Study Sample	Complete final survey	Assume 80% of those enrolling complete final survey	1,000
Objective based on sample size calculation		based on 3 arms of 305 each	915

Source: trial protocol tables google sheet – recruitment objectives

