We will identify a set of patients for recruitment by randomly choosing a subset of approximately 10,500 patients from those who are eligible for recruitment. We estimate that 20% of those contacted will choose to access the enrollment portal. Among those who access the enrollment portal, we estimate 30% attrition based on ineligibility or lack of consent. Finally, we estimate that 60% of those who enroll will complete the final survey in January. The table above identifies the effects of each these assumptions on our final sample size.

We estimate the size of the final study sample will be 1,000 people with 333 assigned to each arm. Our sample size calculations indicate that we need 305 people per arm to have adequate sample size (see detail under section “assessments”).

H. Randomization

We will randomize those who enroll in the study into two treatment arms and one control arm in which they will be directed to different on-line tools. Participants will be randomized at the time they enroll by simply assigning them sequentially to the three arms as they consent.

I. Retention

While our study period is relatively short, only lasting throughout the open enrollment period, a key issue in retention is encouraging people to participate in a survey at the end of the open enrollment

period. Study participants will receive their \$50 gift certificate from Target after completing the post open enrollment survey in January.

J. Intervention

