August 1 – October 14 – recruitment and enrollment

August 1 – website available with “coming soon” information

August 1-August 30 – complete testing and list of changes to developer

September 30 – all changes implemented

October 1 – generate dataset of all [REDACTED] information for everyone chosen for recruitment.

October 1 – October 12 – final verification of functionality

October 15 – e-mail reminder (exact date depends on when tool is refreshed with 2016 open enrollment information)

October 15 – December 7 – Open enrollment – tool available

December 8 – e-mail follow up survey

January 4 – e-mail reminder about survey

December 8 – January 15 – follow up survey open

January 16 – e-mail gift cards

2. Statistical Plan

Sample size calculations:

	Hypothesis						
Outcome	Relative to control, treatment groups will have:	Baseline rate	SD	Change	Power	N per group	Notes:

Plan switching	Higher rates of plan switching	13.6		8.704	80%	305	Kling et al find 28% of people in treatment group relative to 17% in control. Ketcham et al 2013 find relative high rates of switching among new enrollees - 33% between 2009 and 2010 and that switching rates increased over time. KFF (2103) finds 13.6 among all ages in PDP plans. Change is Kling effect of 65% change applied to KFF baseline rate.
Satisfaction with choice process	Greater satisfaction with the choice process	2.6	1.03	0.6	80%	50	Scale of 1-4 in preliminary study with 1 as very satisfied. Data represent means of medicare versus all vendus arms where medicare is the baseline.
Decisional conflict	Less decisional conflict						
Coverage	enrollment in plans that coverage current drugs more generously	368	286	74	80%	236	Based on Kling et al
Coverage (alternative)	Increase in coverage generosity from last years to this years plan	-129	588.42	-543	80%	20	Based on Fall 2015 Results

Analyses:

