For aims 1 and 2, we will compare outcomes between each treatment group and the control group, defining the study population as those who enroll in the study through the enrollment portal and are randomly assigned to a study arm. The main focus of our analyses will be the comparison of the Expert arm relative to the control arm. We will calculate differences in means and proportions using t-tests and chi-squared tests based on the type of study outcome. We will also test the expert arm relative to the treatment arm without expert recommendations to identify the independent effect of expert recommendations. We will develop unadjusted estimates of the treatment effect as well as estimates adjusting for individual characteristics from survey and administrative data.

For aim 3, we will analyze how individual characteristics affect whether people choose to participate in the trial (take up of our invitation to participate). The key study variables will include age, use of myhealthonline, and prescription drug profile.

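### All four primary outcomes need one e-mailed survey, yet the timeline lists a single reminder on day 27 of 38 and the completion assumptions conflict; two more reminders are a cheap safeguard

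*Combined protocol and SAP*

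**What the plan says.** **Source of the outcomes.** In the combined protocol and SAP, Section 1.K, Table 2 takes satisfaction with the choice process and decisional conflict from the survey after open enrollment. The 2017 plan, needed for switching, and the chosen plan, needed for the spending comparison, come from the same survey. Switching also uses the 2016 plan from the enrollment app, and spending uses plan-cost data, but neither can be computed without the survey answer.

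**Survey schedule.** Section 1.M has the survey e-mailed on December 8. The window is "December 8 – January 15 – follow up survey open", and the one survey reminder is "January 4 – e-mail reminder about survey". Section 1.I says that "a key issue in retention is encouraging people to participate in a survey", and ties the $50 gift certificate to completing it.

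**Completion assumptions.** Section 1.G, Table 1 uses 40% attrition among those who open the enrollment app and then "Assume 80% of those enrolling complete final survey". The text after the table uses 30% attrition and 60% completion. It says the table shows the effect of its assumptions, and still projects 1,000 completers. The target is 915, "based on 3 arms of 305 each".

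**The concern.** A participant who does not return this one survey contributes to none of the four primary outcomes. The plan recognizes survey response as the main retention problem, but the listed follow-up is thin. Someone who overlooks the December 8 e-mail is not prompted again for nearly four weeks, and no prompt is listed after January 4.

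Two things are at stake. The first is the number of completers, and so the power for plan switching, the outcome that sets the sample size. The second is recall: satisfaction and decisional conflict concern a choice made between October 15 and December 7. A person who responds only after the January 4 reminder answers at least 28 days after open enrollment closed, and up to 81 days or more after it opened.

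The Analyses part of Section 2 defines the study population as everyone enrolled and randomized. It gives no method for missing survey answers beyond adjusted estimates, so obtaining the answers is the main protection.

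**Working it through.** **1. Timing.** December 8 to January 4 is 23 + 4 = 27 days. December 8 to January 15 is 23 + 15 = 38 days. The reminder therefore falls on day 27 of 38, 11 days before closing.

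**2. The plan's own sample size.** Inputs from the table in Section 2: control switching rate p1 = 0.136 (the source "finds 13.6 among all ages in PDP plans"), change 0.08704, so p2 = 0.22304; power 80%. Alpha is not stated, so I assume 0.05 two-sided. With pooled variance and no continuity correction:

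n = [1.960·√(2·p̄·(1−p̄)) + 0.842·√(p1(1−p1) + p2(1−p2))]² / (p2−p1)², with p̄ = 0.17952

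= [1.960 × 0.5428 + 0.842 × 0.5393]² / 0.08704² ≈ 304.02, rounded up to **305**.

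This matches the plan and supports the alpha assumption (one-sided would give 240). Three arms give 915.

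**3. Completers under each set of assumptions.** Completers = mailed × 0.20 × (1 − attrition) × completion. The completion needed is 915 / enrolled.

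| Assumptions | Mailed | Enrolled | Completion assumed | Completers | Per arm | Completion needed |
|---|---|---|---|---|---|---|
| Table 1 | 10,417 | 1,250 | 80% | 1,000 | 333 | 73.2% |
| Text | 10,417 | 1,458 | 60% | 875 | 292 | 62.7% |
| Text | 10,500 | 1,470 | 60% | 882 | 294 | 62.2% |

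On the text's assumptions the shortfall is 915 − 882 = 33 to 915 − 875 = 40 people, or 33/1,470 = 2.2 to 40/1,458 = 2.7 points of completion. The 1,000 completers that the text projects follow only from Table 1's rates.

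**4. Power.** For switching, power = Φ{[(p2−p1)·√n − 1.960·√(2·p̄·(1−p̄))] / √(p1(1−p1) + p2(1−p2))}. For the two means I used the change and SD in Section 2: 74 and 286 for coverage, 0.6 and 1.03 for satisfaction.

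| n per arm | Switching | Coverage | Satisfaction |
|---|---|---|---|
| 333 | 83.5% | 91.6% | over 99% |
| 305 | 80.1% | 89.2% | over 99% |
| 294 | 78.7% | 88.0% | over 99% |
| 292 | 78.4% | 87.8% | over 99% |

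The decisional conflict row in Section 2 is empty, so its power cannot be computed.

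**5. What a gain would be worth.** The documents give no response gain per reminder. As an illustration only, three points on the text's enrollment is 0.03 × 1,458 ≈ 44 completers, and 875 + 44 = 919, which restores 915.

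**The case against.** The strongest case against has four parts.

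**The shortfall is small or absent.** Under Table 1 the target is exceeded; under the text the gap is 33 to 40 people. This stands. A reader might set Table 1's required 73.2% against the text's 60%, and infer 0.60 × 1,250 = 750 completers, 250 per arm and 72% power for switching. The documents do not support that pairing: the 60% belongs with 30% attrition, where only 62% to 63% is needed. Even at 250 per arm, coverage would keep about 82% power and satisfaction over 99%.

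**The timeline may not list every e-mail.** Section 1.G promises messages about tool access that Section 1.M omits, so silence there does not prove that no further survey reminders would go out. This is fair. But no section mentions another survey reminder, and the schedule as written contains one.

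**The benefit is not demonstrated.** This also stands. A reader might infer that extra reminders would secure power and cut non-response bias. No figure in the documents shows either. A higher overall response does not by itself equalize response between arms, and nothing in the documents shows that it would differ by arm.

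**The schedule is defensible and the recall argument cuts both ways.** The $50 payment depends on completion, and the protocol twice places the final survey in January, so January 4 fits its plan. A prompt near the close would bring in the latest answers, with the longest recall. The recall benefit therefore applies only to people prompted in December. The separate intervention survey also asks about satisfaction and decision conflict at the time of use, but Table 2 does not make it the primary source, and it does not supply the 2017 plan.

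None of this makes the added reminders harmful.

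**Conclusion.** The point holds as a low-cost improvement. Every primary outcome depends on one e-mailed survey, and the only listed survey reminder comes on day 27 of 38. It would be wrong to say that nobody is prompted before the survey closes: January 4 is such a prompt. What is missing is any prompt in December and any in the closing days.

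The size depends on which recruitment assumptions are meant. Table 1 leaves a surplus of 85 completers (1,000 − 915). The text leaves a deficit of 33 to 40 and about 78% to 79% power for plan switching. Only switching falls below 80%, and only slightly. These power figures assume a two-sided 0.05 test without continuity correction, which the exact match to 305 supports but the plan does not state. The response gain from extra reminders is an assumption throughout.

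**What to change.** 1. In Section 1.M, add two automated e-mails to participants who have not completed the survey: one about a week after December 8 and one a few days before January 15. Keep the January 4 reminder, and use the same schedule in all three arms.
2. In Section 1.G, reconcile Table 1 (40% attrition, 80% completion) with the text below it (30%, 60%), and state the completion rate then needed for 915: 73.2% on Table 1's enrollment, 62% to 63% on the text's.

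The cost is two automated e-mails, an edit to the timeline and the recruitment text, slight added burden on participants, and possibly a minor ethics notification. The reminders should not be presented as a remedy for differential non-response between arms.

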Note: Primary study outcomes are italicized and bold.

Outcome Type		Measures	Data Source
Patient Satisfaction	Aims 1 and 2	• Satisfaction with choice process	Post-enrollment survey (primary)
Plan Choice	Aims 1 and 2	• Change in Part D plan chosen	2016 plan from enrollment app and 2017 plan from post

			open enrollment survey. Also question in post enrollment survey about “did they change their plan?”
	Aims 1, and 2	
 • Indicator of enrollment in lowest cost plan* • Indicator of enrollment in expert chosen plan* 	2017 plan from post open enrollment survey and information on OOP cost from [REDACTED] collected in admin panel.
Spending on prescription drugs	Aims 1, and 2.	
 • Difference in spending between lowest cost plan and chosen plan* 	[REDACTED] information for all plans and indicator of which plan was chosen from post open enrollment survey.
	Aims 1 and 2	
 • Difference in spending between 2016 plan and 2017 plan based on initial drug list.* 
Note: this address whether they switched to a lower cost plan
	[REDACTED] information for all plans and indicator of which plan was chosen from post open enrollment survey and which plan they were initially enrolled in from enrollment app.
Choice Experience	Aims 1 and 2	
 • Decisional Conflict • Knowledge about Part D program • Sources of information used • Time spent making decision 	Post-enrollment survey
		
 • How satisfied were you with the process of choosing a plan? • Decision confidence • Decision conflict • Choice knowledge – understanding of features of chosen plan • Right amount of information • Define user monitoring outcomes 	Intervention survey

* Note that calculating these variables requires a drug list for each person. For all people, we can construct an initial drug list based on the data in the EMR. For a subset of people who we observe using the tool, we can construct a revised drug list based on their activity in the tool. All these outcomes are based on the initial drug list.

L. Data Management

See data flow chart document.

M. Study Timeline

May 31 – Large dataset of test data

June 30 – UI changes implemented

July 15 – refreshed study data available to developer

July 31 – administrative console implemented

August 1 – Invitations mailed to participant

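### The coverage row does not say whether its effect of 74 was re-based as the switching effect was; show the sensitivity, and adjust the coverage analysis for each person's baseline spending gap

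*Combined protocol and SAP*

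**What the plan says.** The sample size table in section 2 (Statistical Plan) has two rows that draw on the same cited trial, a paper-letter intervention.

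- **Switching.** The row reads "Higher rates of plan switching 13.6 8.704 80% 305". Its note reports that the cited trial found "28% of people in treatment group relative to 17% in control", and explains that this relative effect was applied to a lower baseline taken from another source.
- **Coverage.** The hypothesis is "enrollment in plans that coverage current drugs more generously". The inputs are baseline 368, SD 286, change 74 and 80% power, giving 236 per group. The note only attributes the row to the cited trial. It names no second baseline, gives no currency unit, and does not say whether 74 is that trial's own effect or a rescaled one.

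Section 1.G concludes that "we need 305 people per arm to have adequate sample size" and expects about 333 completers per arm. Section 1.K says the sample size was chosen to power the primary outcomes. Table 2 there marks the gap between chosen-plan and lowest-cost-plan spending as primary, and its footnote on the spending outcomes says: "All these outcomes are based on the initial drug list".

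The Analyses paragraph plans t-tests for means, plus unadjusted and adjusted estimates. It does not say which estimate is the main one, and it names no baseline spending covariate.

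**The concern.** With the drug list fixed, a person who stays in the same plan has the same calculated 2017 spending whichever arm they are in. The lowest-cost plan on that list does not depend on arm either. A difference between arms in chosen-minus-lowest spending can therefore arise only through plan changes, either more of them or better ones. The Background section describes the same route: lower switching costs lead people into better-covering plans.

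The switching row assumes less switching than the cited trial saw in both arms: 13.6/17 = 0.80 in control and 22.304/28 = 0.797 in treatment. If 74 is that trial's own mean effect, keeping it unchanged means that each switch saves more here than it did there. The plan does not say so or give a reason.

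At stake is whether 305 per arm gives the stated 80% power for coverage as well as for switching.

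**Working it through.** **Inputs.** From the sample size table: change 74, SD 286, switching 13.6% plus 8.704 points, and cited-trial rates of 17% and 28%. From section 1.G: 305 and 333 per arm. The plan states no alpha. Two-sided 0.05 is assumed because it reproduces both stated sizes; one-sided 0.05 would give 185 and 240.

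**1. Reproduce the plan's figures.** For two means, n = 2(1.960 + 0.842)² SD²/d².

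- Coverage: 15.70 × 286²/74² = 234.5, so 235. The t-based solution is 235.4, so 236, as stated.
- Switching, 13.6% against 22.304% (pooled, no continuity correction): 305, as stated.
- Power at 305 for a change of 74: 74/286 × √(305/2) − 1.96 = 1.235, which is 89%. At 333 it is 92%.

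**2. Smallest change with 80% power.** At 305: 286 × 2.802 × √(2/305) = 64.9, which is 12% below 74.

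**3. Scaled scenario.** Assume that 74 was not rescaled, that the gain is proportional to switching, and that the SD stays at 286. The factor is 8.704/11 = 0.791 by added switching, or 13.6/17 = 0.80 by baseline.

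| Change | N per arm, normal / t | Power at 305 | Power at 333 |
|---|---|---|---|
| 74 (as stated) | 235 / 236 | 89% | 92% |
| 74 × 0.80 = 59.2 | 367 / 368 | 72% | 76% |
| 74 × 0.791 = 58.6 | 375 / 376 | 71% | 75% |

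**4. What the scenario implies per switcher.** If 74 arises wholly from added switchers, it is 74/0.11 = 673 each in the cited trial. Keeping 74 with 8.704 points needs 74/0.08704 = 850 each, 26% more. The 80% threshold needs 64.9/0.08704, about 745 each, 11% more.

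**5. Sensitivity to the SD (factor 0.791).** If the SD shrinks in proportion to the effect, N stays at 235. If it shrinks with the square root of the factor, N is 297 and power at 305 is 81%. With the change at 58.6, 80% power at 305 needs an SD of about 258, roughly 10% below 286.

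**6. Gain from baseline adjustment.** Adjusting for a covariate with correlation r to the outcome multiplies the required N by (1 − r²). Setting 376(1 − r²) ≤ 305 gives r² ≥ 0.189 and r ≥ 0.435, so about 0.44. On the switching row's own figures, 86.4% of controls and 77.7% of treated participants stay in their plan, and stayers largely keep their gap. A correlation of that size is therefore plausible, but the documents report none.

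**The case against.** A reader might infer that coverage really needs 375 per arm instead of 236, that coverage and not switching sets the sample size, and that 305 is underpowered. The documents do not support this, for five reasons.

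- The 236 follows from the row's own inputs.
- The text does not show that 74 is the cited trial's raw effect, and this cannot be checked without the source.
- The switching row keeps the trial's relative effect and replaces the baseline. Multiplying 74 by a ratio of switching rates is a different rule. The plan's rule applied to coverage needs a local coverage baseline, and the only one given is 368, where the change stays 74 (20.1%). It could even point the other way. At an assumed 673 per switcher, 3.4 points less control switching raises the baseline gap to about 391. Then 20.1% of that is about 79, and 305 gives about 92% power.
- A web tool with automatic drug import and expert scores may save more per switcher than a letter, and the SD may not stay at 286.
- Section 1.C words this primary outcome as a change in generosity. That is closer to the alternative coverage row (change −543, SD 588.42, N 20) than to the gap marked in Table 2.

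These points defeat the inference, and the first two stand in full. They do not remove the unexplained difference between the two rows. The SD point is only partly persuasive: the Table 2 outcome is a level whose SD includes variation among stayers, so shrinkage in full proportion to the effect is unlikely. The alternative row measures something else and does not show how 74 was derived. The planned adjusted estimates go part of the way, but the most useful covariate is not named.

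**Conclusion.** The coverage row is arithmetically correct. What remains is an unstated assumption: one effect from the cited trial is visibly moved to a lower baseline, and the other is not.

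The 80% claim at 305 holds for coverage if the true change is at least about 65 with SD 286. Power is 89% at the stated 74. It is about 71 to 72% if 74 is unscaled, the gain shrinks with switching, and the SD is fixed. Those three conditions are assumptions, and so is two-sided 0.05. The point also depends on reading the chosen-minus-lowest gap in Table 2 as the coverage outcome that this row powers.

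This is an improvement available at no cost in patients or data. It is not a finding that the stated sample size is wrong.

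**What to change.** 1. **Sample size table.** Keep 236 for a change of 74. State whether 74 was rescaled. Add the range: a change of about 59 needs about 367 to 376 per arm and gives about 71 to 72% power at 305, and about 65 is the smallest change with 80% power there.
2. **Analyses paragraph.** Make the main analysis of chosen-minus-lowest-cost spending a linear regression on arm, adjusted for each person's baseline gap (2016 plan minus lowest-cost plan on the initial drug list). Report the unadjusted t-test as supportive. State which plan year's prices define the baseline gap.

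The inputs are already collected: the 2016 plan in the enrollment portal (section 1.G), the drug list from the medical record (Table 2 footnote), and the vendor's plan costs (Table 2 and section 1.M). The cost is one table note and one or two sentences in the Statistical Plan. No patients, visits or survey items are added. The sponsor would be showing a less favourable scenario beside the stated one.

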In our ethnographic study, older adults also expressed interest in having additional support, often indicating they would like the help of an expert, such as an insurance broker or other type of knowledgeable individuals.

Our study is based on the hypothesis that these barriers create switching costs for beneficiaries and that removing these barriers would lower switching costs making beneficiaries more likely to evaluate their alternatives and to enroll in plans that provide better coverage for the drugs they are likely to use. We also hypothesize that reducing switching costs, particularly by providing expert recommendations, will reduce decisional conflict and create greater satisfaction with the choice process.

While the tool we have designed in partnership with patient stakeholders is easier to use than the Medicare.gov website, it provides less detail on how the different plans cover particular types of drugs. In our qualitative work examining the use of the first version of our tool, we found that its simplicity was more attractive to some people than others. Thus, we will examine particular characteristics of individuals including numeracy, "do-it-yourselfness", and satisficer/maximizer behavior influence how people evaluate the decision process in the different tools.

A final issue in this context is whether simply providing access to web-based decision support tools is likely to assist the types of people who experience the greatest difficulty in decision-making. We will examine the take-up of decision support in this setting to determine how well targeted it is by analyzing who chooses to enroll in our trial and among those who enroll, who uses the study intervention.

E. Participants

Our study population will include PAMF patients aged 66 to 85 who were enrolled in Part D coverage during 2016. We plan to have a final study sample of at least 915 people with complete data on study outcomes.

F. Screening

We will prescreen patients using administrative data to identify potential study participants based on whether they are enrolled in Medicare, their age (66-85), whether they live in the primary PAMF service area (county=Santa Clara, San Mateo, Santa Cruz, and Alameda), and whether they have active medication orders in the PAMF EMR. We will also exclude patients enrolled in MediCal or a Medicare Advantage plan in 2016. In preliminary analyses, we have identified 46,525 PAMF patients who meet these criteria.

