An important sampling issue for our study is whether people are married or cohabitating. Randomizing people who are cohabitating to different treatment arms could lead to cross-arm contamination, potentially diluting the treatment effects. We will prescreen patients for cohabitation/marital status based on patient residence and phone number. We will then randomly choose one member of each household to participate in the intervention. In our preliminary analysis, we excluded an additional 7,659 people using this method. Because this represents fewer people than we would have expected based on national rates of marriage among older adults, we will also screen for cohabitation when recruiting. Again, based on our preliminary analysis, there will be 38,866 remaining patients eligible for recruitment.

G. Recruitment

We will recruit a subset of those patients eligible for recruitment with a goal of obtaining complete study data from 915 patients. We will identify a set of patients for recruitment by randomly choosing a subset of approximately 10,500 patients from those who are eligible for recruitment. For the patients targeted for recruited (recruitment sample), we will send them a letter in August introducing the study and inviting them to participate. The letter will inform the respondent that they have been selected to participate in a study of the effects of providing personalized information on Medicare Part D prescription drug plans and that they will be randomized to different arms representing different ways of providing that information, that participation in the intervention will allow them to easily access information from PAMF on the prescription drugs they are currently using. The e-mail will also inform the patients that they will receive a \$50 electronic Target gift certificate at the end of the open enrollment period for participating in the study following the completion of a questionnaire. The letter will direct participants to a website (enrollment portal) where they can check if they meet the eligibility criteria and, if so, enroll in the study and provide informed consent.

The initial invitation will include a study ID that the participant will use to enter the enrollment portal. This ID will be used as their study ID throughout the study and will be used to link data from their medical records to data gathered as part of the study. The enrollment portal will have 4 functions:

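### The recruitment text (30% attrition, 60% completion) contradicts Table 1 (40%, 80%) and yields 882 completers, not the stated 1,000 or the 915 target; the handling of missing survey outcomes is also unstated

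*Combined protocol and SAP*

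**What the plan says.** **Recruitment assumptions (section G).** Table 1 starts from 10,417 mailed and assumes that 20% check their eligibility. It continues with "Assume 40% attrition among those who access enrollment app" and "Assume 80% of those enrolling complete final survey", arriving at 1,250 enrolled and 1,000 in the final sample. The paragraph after the table starts from about 10,500 invitations and also assumes 20% portal access. It then says "we estimate 30% attrition based on ineligibility or lack of consent" and "Finally, we estimate that 60% of those who enroll will complete the final survey in January". It refers to the table for the effect of these assumptions and gives 1,000 people, 333 per arm, against a requirement of 305 per arm.

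**Target.** Section E says "We plan to have a final study sample of at least 915 people with complete data on study outcomes". Section G repeats it: "with a goal of obtaining complete study data from 915 patients". The target is thus already counted in completers.

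**Population and outcomes.** The Analyses section of the Statistical Plan compares arms for aims 1 and 2 "defining the study population as those who enroll in the study through the enrollment portal and are randomly assigned to a study arm", using t-tests, chi-squared tests and adjusted estimates. Table 2 (section K) takes satisfaction and decisional conflict from the final survey. Switching and coverage need the 2017 plan, which Table 2 also takes from that survey. Section C mentions administrative data as well, but Table 2 names no administrative source for the 2017 plan. No section says what happens when the survey is not returned.

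**The concern.** The two sets of rates cannot both describe the trial. The expected final sample is what the plan sets against its 915 target, and a reader cannot tell whether 20% or 40% of enrolled people are expected to lack primary outcomes. If the text is right, 10,500 invitations do not reach the target. If the table is right, they do, with some margin.

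The same uncertainty carries into the analysis. A participant who does not return the final survey has no value for any of the four primary outcomes, so the planned tests can use completers only. If response is related to the outcome, the completer difference may not be the difference among everyone assigned. The plan gives no way to judge how far a result would depend on that.

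**Working it through.** **Inputs.** Invitations: 10,417 (Table 1) or 10,500 (text). Portal access: 20% (both). Attrition: 40% (Table 1) or 30% (text). Completion: 80% (Table 1) or 60% (text). Switching: 13.6% baseline plus 8.704 points, so 22.304% (sample size table), with 80% power. The plan does not state alpha; two-sided 5% is assumed because it reproduces the plan's figure.

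**Step 1: reproduce 305 per arm.** With p1 = 0.136, p2 = 0.22304 and mean p = 0.17952:

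n = [1.96 × √(2 × 0.17952 × 0.82048) + 0.8416 × √(0.136 × 0.864 + 0.22304 × 0.77696)]² / 0.08704²
= [1.0638 + 0.4538]² / 0.007576 = 304.02, rounded up to 305. This matches, and 3 × 305 = 915.

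**Step 2: reproduce Table 1.** 10,417 × 0.20 = 2,083; × 0.60 = 1,250; × 0.80 = 1,000 (333 per arm). This matches.

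**Step 3: apply the text's rates to the text's invitations.** 10,500 × 0.20 = 2,100; × 0.70 = 1,470; × 0.60 = 882 (294 per arm). This is 118 short of 1,000 and 33 short of 915. At these rates, 915 completers would need 915 / (0.20 × 0.70 × 0.60) = 10,893 invitations, and 1,000 would need 11,905.

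**Step 4: all combinations from 10,500 invitations.** Power = Φ[(0.08704 × √n − 1.0638) / 0.5393].

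| Attrition | Completion | Completers | Per arm | Power, switching |
|---|---|---|---|---|
| 40% | 80% (Table 1 rates) | 1,008 | 336 | 84% |
| 30% | 80% | 1,176 | 392 | 89% |
| 30% | 60% (text rates) | 882 | 294 | 79% |
| 40% | 60% | 756 | 252 | 72% |

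At Table 1's own 333 per arm, power is 83.5%.

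**Step 5: missing outcomes.** Table 1: 1,250 − 1,000 = 250, about 83 per arm (20%). Text: 1,470 − 882 = 588, or 196 per arm (40%).

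**Step 6: tipping point for switching.** Suppose completers show exactly the planned 22.304% against 13.6%, and control non-responders also switch at 13.6%. Let nc be completers and m non-responders per arm, with q the switching rate among treatment non-responders. The treatment rate over all assigned is (0.22304 × nc + q × m) / (nc + m), compared with 0.136. Solve for the q at which the pooled z equals 1.96. The lower end of each range bases the variance on all assigned; the upper end bases it on completers only.

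- 80% completion (nc = 333, m = 83): significance is lost if q falls below 3.7% to 6.9%. At q = 13.6% the difference is 7.0 points and z is 2.67 to 2.39.
- 60% completion (nc = 294, m = 196): significance is lost if q falls below 12.0% to 15.6%. At q = 13.6% the difference is 5.2 points and z is 2.22 to 1.72.

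At 80% completion, treatment non-responders would have to switch at roughly half the control rate or less to overturn the result. At 60%, switching at about the control rate could be enough.

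**The case against.** **Power.** The 915 target already counts completers, so Table 1 allows for non-response. Even on the text's rates the loss is about one percentage point of power. This stands. The defect in the funnel is the contradiction and the unreachable 1,000; a reader who infers that the trial is badly underpowered goes beyond the documents.

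**Population wording.** It is tempting to see a conflict between the all-assigned population and the complete-data sample. Table 1 names the enrolled population and the study sample separately. The Analyses wording can be read as saying whom the trial compares, by assignment and regardless of tool use, while sections E and G say how many must have data. These can coexist; what is missing is the rule that links them. Likewise, section G already deals with people who are not the sole household representative: they keep access, "based on the single representative but will exclude them from data analysis". That criterion is set before assignment, so its absence from the Analyses section is editorial.

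**Bias.** A reader might infer that completer comparisons will be biased. The documents do not support that. Nothing in them suggests that response differs by arm or by switching, and the gift certificate and survey reminder are the same for all arms. Response that depends on switching equally in both arms creates no bias when there is no effect. Any figure for the bias would rest on invented response rates, so none is offered here.

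**Adjusted estimates.** These are planned, but the covariates are not named and adjustment is not presented as a way of handling non-response. They do not close the gap.

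**Conclusion.** The funnel contradiction is wrong as written. The text's rates give 882 completers (294 per arm, about 79% power for switching), not the stated 1,000, and fall short of 915; only Table 1's rates give 1,000. The power figures assume a two-sided 5% test without continuity correction, which reproduces the plan's 305.

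The missing-outcome point is smaller and is mainly an unstated rule. The primary tests will in effect be completer analyses, with 20% of outcomes missing under Table 1 or 40% under the text. Under Table 1 this is a matter of possible bias, unknown in size and direction, and not of lost power. For switching, a result equal to the planned effect would be fairly robust at 80% completion and fragile at 60%, assuming control non-responders switch at 13.6%. The other three primary outcomes share the dependence on the survey, but nothing has been quantified for them here.

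**What to change.** 1. Reconcile 40%/80% with 30%/60%, and 10,417 with 10,500. Restate expected enrollment, final sample and power from the figures kept. If the text's rates are kept, the stated 1,000 must change, and about 10,900 invitations would be needed to reach 915.
2. In the Analyses section, state that the primary tests use final-survey completers, analysed as assigned.
3. Report the response rate by arm. This describes the problem but cannot exclude response that depends on the outcome itself.
4. Pre-specify one sensitivity analysis for switching: a tipping-point analysis that varies the non-responder switching rate separately in each arm. Optionally add multiple imputation or response weighting using baseline data already planned (Survey 1, age, the drug list from the medical record, myhealthonline use, 2016 plan), noting that it handles only non-response explained by those data.

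The cost is plan wording and modest programming, with no new data collection. The sensitivity analysis may give wider intervals, and a tipping-point analysis shows fragility without correcting it.
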